Although cART suppresses the viral load, it does not eradicate HIV infection, which remains associated with relatively high levels of inflammation that may increase the risk for a range of health problems. Our preliminary data indicates that PLWH who use cannabis on a recreational level show a decrease in chronic inflammation, possibly MAPK-signaling mediated. We hypothesize that CBD is able to reduce inflammation via MAPK-dependent alterations of the circulating monocyte population.

Cannabis sativa (marijuana) and its cannabinoid derivatives, Δ 9-tetrahydrocannabinol (THC) and CBD, are largely used by people living with HIV (PLWH) to stimulate appetite, prevent weight loss (FDA approved Marinol or Dronabinol), or manage chronic pain. CBD is sold in grocery stores in the US. Although beneficial effects of cannabis on inflammation are well known, [2] and despite its widespread use, the differential impact of cannabinoids on health outcomes in PLWH remains understudied.[3] As a consequence, the cannabinoids molecular chain leading to inflammation reduction remains to be unveiled.

Cannabinoids bind to endocannabinoid system receptors CB1R, which is mostly found in the central nervous system, and CB2R, mostly found in your peripheral nervous system, especially immune cells. THC binds to CB1R and CB2R, found on the surface of immune cells and tissues, including T-cells, macrophages/monocytes, and microglia. It is known that monocyte cells treated during differentiation with THC displayed reduced expression of CD14, CD16, and CD163, therefore suggesting a fundamental alteration in phenotype [4]. Our preliminary microarray transcriptome study evidenced that peripheral blood mononuclear cells (PBMCs), obtained from patients using marijuana recreationally, show MAPK-signaling pathway alterations [4]. Based on these results, the long-term goals of this research are to determine whether it is possible to attenuate and possibly resolve chronic inflammation in PLWH with CBD. As a first step, this proposed research will determine cell-type specific CBD mechanisms altering HIV-1 infected cell state at the RNA level, and how these gene expression pattern shifts influence HIV-associated

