persistent inflammation reduction. In other words, we will obtain cell-type specific biomarkers that are associated with inflammation reduction in PLWH after CBD long-term assumption. We hypothesize that CBD reduces inflammation by causing cell-type specific MAPK-dependent alterations of monocyte phenotype, reducing their overall migratory capacity. We will take advantage of the established technique of single-cell RNA sequencing (scRNAseq), that has already been used to quantify the plasticity of immune cell expression profiles [5], including showing how SIV (simian immunodeficiency virus) induces senescence in macrophages [6]. We will investigate cellular type/state alteration using cross-sectional PBMC samples obtained from PLWH that do not use CBD or marijuana and who consent to use CBD for two months to address unanswered questions regarding CBD effects of chronic inflammation: In which cell population is the MAPK-signaling pathway deregulated? How is CBD responsible for immunomodulation? Which CBD mechanism alters the inflammation process? Our team proposes to leverage our existing expertise in HIV genomics/transcriptomics at the single cell level, UF infrastructures, and collaborations to test our hypothesis via the following specific aims.

5. Specific Aims:

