Study Population. Our clinical population will be men and women (N=5 to 7) 21-60 years old who are currently living with HIV (under antiretroviral therapy for 5+ years with a suppressed viral load).

Recruitment strategy. Co-I [name] has extensive experience in HIV patient recruitment and will oversee the recruitment team, during the recruitment phase, as well as the safety monitoring. Five PLWH (men and women) will be primarily recruited from The SHARC Registry (IRB# 201400073), a UF-IRB-approved registry of over 600 HIV patients who have agreed to be contacted about future research. Written informed consent will be obtained, and blood will be collected at the UF CTRB clinical research center. Inclusion criteria are: ability to read English and provide written consent; willingness to take CBD and to participate in follow up for two months; older than 21 and younger than 60; under antiretroviral therapy for 5+ years and suppressed viral load (CD4 count <350cells/ml); patients must agree to practice acceptable methods of birth control, namely sterilization (female tubal ligation or occlusion, male vasectomy), long-acting reversible contraceptives (intrauterine devices, hormonal implants), short-acting hormonal methods (pill, mini pills, patch, shot, vaginal ring), and condoms.

The main exclusion criterion will be conditions/medications that may impair the immune response (e.g. rheumatoid arthritis, cancer, diabetes chronic infections, CAD, cellulitis, autoimmune diseases such as lupus, sarcoidosis, and all medications they may affect inflammation such as aspirin, steroids, statins);), pregnancy, and current marijuana or CBD use (urine drug screen). Further exclusion criteria will be: excluding subjects taking anti-seizure medicines, with any history of seizure disorder or head trauma, any history of hepatic/liver disease or renal disease, any history of cardiovascular diseases; women who are lactating (in addition to existing exclusion criteria for pregnancy). Co-I [name] (a physician) will review conditions/medications after the initial interview before the patient is enrolled to exclude risks of drug interactions or hepatotoxicity. UF/Shands staff and students will not be considered for enrollment. Presence of chronic pain will not be considered as a necessary condition for enrollment.

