Motivation to study single cells. The molecular and cellular changes underlying the inflammation mitigation caused by CBD-administration are largely unknown, and stand as a major challenge both for understanding its basic biology (e.g., pathways involved, molecular mechanisms) and for the urgent unmet need of reducing the long-term harm chronic inflammation causes in PLWH. Our hypothesis is that CBD alters monocyte migration capacity with MAPK-dependent alterations. We expect this alteration to have

chain-effects based on cellular cross-talk, i.e., that different PBMC cell types (such as Tcells and B-cells) might express specific CBD-induced phenotypes. We hypothesize CBD-alterations to reverberate along the whole immune-modulation system through cellular cross-talk. Given the complexity of the immune response, we deem traditional (bulk) RNA sequencing as insufficient for the task. Population-averaged genomic profiling cannot adequately unravel the inter-cellular regulation in situ. This study will leverage the efficiency of newly available single-cell technologies to create a powerful dataset unveiling the functional properties of thousands of individual cells.

Sample collection and processing. We plan to collect samples from five to seven patients over three time points: baseline (no CBD), and after one and two months of CBD-administration with 5,000 cells sequenced per sample. Five to seven patients (15 to 21 samples) will provide the transcriptomes of 75,000-105,000 single cells, a large dataset for scRNAseq. Immediately after collection, samples will be collected by TBD Lab technician to be processed for scRNAseq at UF ICBR (PBMC scRNAseq experiments are routinely run at ICBR).

Data analysis. During the post-processing period, single-cell reads (count matrices) will be filtered for quality control. Unsupervised clustering will isolate statistically robust populations of similar cells. Clusters will be visualized using Principal Component Analysis (PCA), t-Distributed Stochastic Neighbor Embedding (tSNE), and Uniform Manifold Approximation and Projection (UMAP). The most informative gene expression markers will be identified by a host of non-parametric tests (e.g., the Kolmogorov–Smirnov test), comparing a given cluster against either a nearby cluster or all other clusters. Clusters of cells will be annotated by using their marker genes/pathways⁻ and prior biological knowledge to characterize each sample's cell composition.

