Each participant will be provided two 30mL bottles (2000mg CBD per bottle) with a syringe dropper during their initial (baseline) visit with instructions/demonstration to administer the solution under the tongue (0.5 cc ~1/2 dropper) twice per day (BID) 8-12 hours apart (morning and evening) at the prescribed daily dosage (63mg/day). The sublingual route of administration allows the product to be absorbed directly into venous circulation, and thus bypasses the liver and eliminates the consequences of first pass metabolism; ultimately increasing its bio-availability. The bioavailability of CBD administered orally (including sublingual) is estimated to be 13-19% and its half-life estimated to be around 18-32 hours.

Physical Discomforts and Intervention Risks:

In previous clinical trials using hemp-derived products administered orally (liquid or capsule) and swallowed, a small percentage of patients experienced tiredness, change in appetite and gastro-intestinal discomfort following ingestion. We will be using daily doses of hemp extract that are considerably lower than the daily doses used in the clinical trials. Therefore, the chance of our participants experiencing these side effects is minimal.

Occasionally one or more of the following potential side effects of taking blood samples may occur: pain, bruising, slight bleeding, light-headedness, fainting and (rarely) an infection. A trained technician will be drawing the blood.

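### No look-back period is set for cannabis, CBD or inflammation-affecting medicines, so carry-over into each patient's only pre-CBD sample cannot be ruled out

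*Combined protocol and SAP*

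**What the plan says.** **Exclusions.** Section 6, Recruitment strategy, excludes "current marijuana or CBD use (urine drug screen" and, in the same paragraph, "all medications they may affect inflammation such as aspirin, steroids, statins". The first is limited to current use; the second has no time frame. Elsewhere in that paragraph the authors do set a time scope, for example "any history of hepatic/liver disease or renal disease, any history of cardiovascular diseases". The Background describes the population in the present tense, as "PLWH that do not use CBD or marijuana".

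**Checks before enrolment.** There are four.
- A coordinator screens candidates (Experimental Procedures, Screening).
- A study physician "will review conditions/medications after the initial interview before the patient is enrolled to exclude risks of drug interactions or hepatotoxicity" (Recruitment strategy).
- The baseline visit includes a medical history and a review of concomitant medications and eligibility (Safety Monitoring and Stopping Criteria).
- A urine drug test is listed at visit 1, the same visit as the baseline blood draw and the hand-out of the bottles.

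**Reference sample.** Samples are taken at "baseline (no CBD), and after one and two months of CBD-administration" (Sample collection and processing). The section on CBD biomarker extraction contrasts baseline clusters with clusters of the same cell type after CBD. There is no untreated group.

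**Pharmacology and prior data.** For CBD, the dosing section gives "its half-life estimated to be around 18-32 hours". The Background reports preliminary data that "PLWH who use cannabis on a recreational level show a decrease in chronic inflammation".

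**The concern.** Everything the study attributes to CBD is a change from one blood sample per patient. That sample is treated as free of CBD, but the eligibility rule requires only that use is not current. If a patient arrives with recent CBD or cannabis exposure, part of the treated phenotype may already be in the baseline, and the apparent CBD effect would tend to shrink. If a patient has recently stopped a steroid, statin or aspirin, inflammation may change after baseline because that drug's effect is wearing off. With no untreated group, such a change could be credited to CBD or could mask it; the direction is not known.

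The pathway at risk is the one under study. The primary aim is MAPK-linked inflammation markers, and the Abstract and Background report MAPK-pathway findings in cannabis users. The primary-outcome text also regresses gene markers on variation in baseline inflammation, which a recently stopped anti-inflammatory drug could distort. Later samples cannot repair a compromised reference.

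**Working it through.** **1. The plan's own figure.** Samples and cells are patients × 3 time points × 5,000 cells.
- 5 × 3 = 15 samples; 15 × 5,000 = 75,000 cells.
- 7 × 3 = 21 samples; 21 × 5,000 = 105,000 cells.

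Both match the Sample collection section. One of the three samples per patient is pre-CBD, so each patient supplies 1/5 = 20% or 1/7 = 14% of the reference samples. With equal cell yield, each supplies the same share of the pooled baseline cells: 5,000 of 25,000, or 5,000 of 35,000.

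**2. Do the checks set a time window?**
- Urine test: analytes, cut-off and detection window are not stated. The documents do not say whether it detects CBD, or that the result is read before the blood draw.
- Physician review: no window. Its stated purpose is drug interactions and liver toxicity.
- Baseline history and coordinator screening: no window to apply.
- Aspirin, steroids and statins: no test is described, only the reviews above. The gap is clearest here.

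**3. CBD remaining after the last dose.** The input is the protocol's half-life of 18-32 hours. The assumption is first-order elimination, so the fraction remaining is 0.5^(hours / half-life).

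| Time since last dose | Half-life 18 h | Half-life 32 h |
|---|---|---|
| 24 h | 40% | 59% |
| 48 h | 16% | 35% |
| 72 h | 6% | 21% |
| 7 days (168 h) | 0.2% | 2.6% |

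Five half-lives take 5 × 18 = 90 h (3.8 days) to 5 × 32 = 160 h (6.7 days). A window of 7 days covers that range.

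These figures describe CBD only. The documents give no half-life for THC, steroids, statins or aspirin.

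**4. What one affected patient could do to the mean contrast.** Let k of n patients have a baseline that already carries a share f of the CBD effect. The mean contrast is then diluted by k × f / n. The documents give no value for f, so the range 0.25 to 1.0 is an assumption.
- k = 1: 0.25/5 to 1/5 = 5-20% at n = 5; 0.25/7 to 1/7 = 4-14% at n = 7.
- k = 2: 10-40% at n = 5; 7-29% at n = 7.

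This is an illustration of scale. Drug remaining in step 3 is not a measure of f, and nothing in the documents links the two.

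**The case against.** **The screen may catch recent users.** A reader might infer that anyone who stops the day before visit 1 qualifies. The documents do not support that: the criterion itself names a urine drug screen, and use the day before could well give a positive result. A reader might equally assume that the panel looks only for THC and misses CBD. The documents do not say that either. What stands is that the analytes and window are unstated, so the screen's protection is unknown for CBD, and it is not described as covering the medicines at all.

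**Other checks exist.** Urine is not the only safeguard. The interview, physician review and medical history make a last-minute stopper less likely, and a habitual user who paused for a day does not naturally fit the Background's description of non-users. This lowers the probability, but none of these checks gives staff a period to apply.

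**Contamination is not shown.** A reader might conclude that the baseline is contaminated. Nothing shows that a recent stopper will be enrolled. The preliminary data concern people using cannabis recreationally and call the MAPK link only possible; they do not show effects that persist after CBD is stopped.

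**It is a small pilot, and dilution is conservative.** This holds for a claim of benefit from CBD. It helps less in a study meant to discover markers, where dilution means missed markers, and it does not cover recently stopped medicines, whose direction of bias is open.

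**Conclusion.** The concern holds as a gap in the eligibility rule. No look-back is defined for cannabis, CBD or inflammation-affecting medicines, and no listed check supplies one. A recent stopper whom the screen does not catch can be enrolled, and that patient's only no-CBD sample may carry prior exposure. For medicines the exclusion is untimed; it should not be read as limited to current use, because the word *current* applies only to marijuana and CBD.

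The size is bounded only in part. One affected patient is 14-20% of the sample, and CBD could still be present for several days after stopping. The effect on expression or inflammation is not known from the documents, and the 4-20% dilution for one patient rests on the assumed f. The half-life figures rest on first-order elimination and on the protocol's own estimate. The point should be settled before the first baseline draw, because it cannot be corrected afterwards.

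**What to change.** - In the Recruitment strategy, replace *current* with a stated look-back, asked by self-report at screening and kept alongside the urine screen. For CBD, at least 7 days follows from the protocol's half-life.
- For cannabis and for medicines that affect inflammation, state a longer window. Thirty days would match the monthly visit interval, but it is an assumption and should be labelled as one, since the documents give no half-life for these.
- State what the urine screen detects, CBD in particular, and over what period. Read the result before the baseline sample is used.
- Apply the look-back only as a screening criterion, never as a request to stop a prescribed drug. Allow re-screening once the window has passed.

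**Cost.** One line in the criteria and two screening questions. Some candidates will be deferred, by up to a month with a 30-day window. This may be more than a few, because the Background says cannabis and its derivatives are widely used by people living with HIV, and the medicine exclusion includes aspirin. The registry of over 600 for 5-7 places should absorb this, though the documents do not say how many registrants would be affected.

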Overview and Rationale for Study. Inflammation is a primary HIV-related complication. HIV patients experience non-AIDS-related complications that are typical of older patients, such as presence of neurocognitive disorders, metabolic syndrome, bone abnormality, non-HIV-associated cancers, and neurocognitive disorders [1]. Chronic inflammation in PLWH is a significant problem that impacts the quality of life in PLWH. The effects of cannabinoids in reducing inflammation are renowned; however, the intra-cellular mechanisms and pathways that cannabinoids use to alter inflammation are yet to be discovered. Our central hypothesis is that CBD is an extremely beneficial therapeutic drug for PLWH, because it reduces inflammation by hindering pro-inflammatory monocytes via MAPK-dependent pathways. This hypothesis targets two fundamental unanswered problems in the field of HIV/AIDS, that are high HIV/AIDS NIH priorities: (i) identifying the mechanism regulating PLWH persistent inflammation, which in turn plays a pivotal role in all the main causes of death in PLWH; and (ii) investigating the role of cell-specific candidate biomarkers describing the molecular response to CBD, which may open for new cure strategies.

By mapping the effects of a controlled trial of CBD-administration at the single-cell level, we will pave the way for new candidate therapies, from CBD- and other cannabis-based therapies to the identification of novel protein targets for drug repurposing or discovery. Understanding how CBD reverses inflammation (potentially at the systemic level), will help overcome a significant challenge for HIV care and treatment, particularly for infected young adults who have a lifetime in combined antiretroviral therapy (cART). Filling this gap is particularly relevant because our findings will provide a framework for the evolving policies for clinical use of FDA-approved drugs for HIV cure strategies. As such, it has an enormous repercussion as THC is not legalized for its psychoactive properties, while CDB can be found in any grocery store in the US. Therefore, understanding CBD influence on HIV-induced inflammation is also extremely important to inform the medical community and the public answering which compound has a therapeutic validity. Our findings will potentially open a new therapeutic window for personalized and precision medicine.

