The main objective of this project will be to identify inflammatory reduction biomarkers linked to MAPK-dependent alterations after CBD administration, as well as other systemic effects on cell signaling pathways. Investigating the role of cell-specific biomarkers describing the molecular response to CBD-administration may open avenues for additional therapeutic strategies that can help reduce the burden of chronic musculoskeletal pain and other pain-related symptoms and comorbidities in people living with HIV (PLWH). The team proposes to study the effects of CBD on inflammation and chronic pain in PLWH by enrolling five persons with HIV who will provide blood samples before and after taking CBD for two months. In the process, the goal will be to establish the molecular role(s) of different immune cells using single cell RNA-sequencing. Preliminary data from this study are expected to pave the way for further investigations in larger clinical cohorts. The primary aim of this project will be to identify key inflammatory reduction biomarkers linked to MAPK-dependent alterations after CBD administration. Secondary outcomes include pain relief and reductions in pain-related symptoms. We will use a prospective pilot study design where patients will self-administer the investigational product (CBD-extract) for 60-days (2 months).

Specific Aim #1 – Determine the effects of CBD on chronic on quality of life in PLWH. We will compareQuality of Life (QoL) measures between treatment conditions, including pain and pain-related symptoms, if present.

Specific Aim #2 – Determine key biobehavioral mechanisms contributing to antiinflammatory and analgesic effects of CBD administration in PLWH. We hypothesize that change in molecular (alterations in cell signaling and reduction in inflammatory cytokines), psychological (reduction in pain-related fear and pain catastrophizing), and pain sensitivity regulation measures will be associated with pain relief, inflammation reduction, and reservoir shrinkage. We will quantify the shift in anti-inflammatory macrophage/monocyte population caused by CDB administration by examining gene expression at the single-cell level from the PBMC samples. This will allow us to accurately pinpoint gene under- or over-expression patterns at the RNA level (biomarkers), that are both induced by CBD administration in PLWH, and specific to different cells (e.g., monocytes, T cells, B cells, or other immune cells).

6. Research Plan

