CBD biomarker extraction. We will contrast clusters of the same cell type at baseline (no CBD) and their counterparts after CBD administration. The difference in gene expression, measured in fold change, p-value, and ratio of cell fraction expressing the marker gene, will determine the phenotypic effect of CBD. For each cell type, we expect to extract one or more sets of CBD-specific candidate biomarkers that together will determine a phenotypic CBD per cluster (cell type) signature.

Investigational Product & Dosing Schedule. [name] (Co-I) will oversee CBD dosage and administration.We will source the investigational product from the same batch of our hemp-extract CBD product that is being used in the original protocol under IND 147985, 'Efficacy of a controlled short-term trial of Cannabidiol (CBD) ingestion on reducing symptomatic response and facilitating recovery after induced muscle injury' (Source: SunFlora, Inc, [name])''. SunFlora is a third-party tested hemp-derived product manufacturing company. SunFlora is dedicated to producing high quality hemp-derived products formulated to be safely used by the public and are manufactured in accordance with the Food and Drug Administration (FDA) Current Good Manufacturing Practices (cGMP) for Dietary Supplements, 21 CFR Part 111. Their hemp derived products are assessed multiple times at production process control points throughout the manufacturing process. Dietary ingredients used in the manufacturing process are accompanied by certificates of analyses (CoAs) confirming their identity and specifications. All finished products are tested to ensure they meet specifications prior to being released for distribution. The label and all labeling satisfy FDA requirements found under 21 CFR 101.

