Primary Outcomes: This study takes a single-cell perspective, i.e., we will collect a large number of cells from a small number of patients, and we will measure RNA expression per single cell (not per patient). Note that from the single cell point of view, the number of patients (5-7) is sufficient to derive statistically viable results, as we will collect 5,000 cells from each patient at each time point (total 75,000-105,000 cells). Each cell will be sequence individually to read the RNA expression from a panel of approximately 20,000 genes. Cells will be pooled from all patients, and clustered via unsupervised algorithms into clusters of different cell types (e.g. T cells, B cells, monocytes). Our primary outcomes will be the extraction of gene expression patterns (RNA) from specific immune cell types found in PBMC (e.g., B cells, T cells, monocytes). We will regress these gene markers against the variation in baseline inflammation (C-reactive protein, erythrocyte sedimentation rate, and procalcitonin). After CBD administration to obtain CBD-related biomarkers for inflammation reduction. The difference in gene expression will be measured in fold change, p-value, and ratio of cell fraction expressing the marker gene. These biomarker gene will be unique for each cell type. We expect to extract specific biomarkers for each cell type and understand how CBD alters gene expressions of different immune cells in a different way-overall, we expect the genes of the MAPK signaling pathway (MAPK families play an important role in complex cellular programs like proliferation, differentiation, development, transformation, and apoptosis) to be strongly altered.

Secondary Outcomes. Self-report pain ratings will be used to determine peak pain intensity and pain persistence. The brief pain inventory (BPI) will be used to self-report pain perception. The inventory consists of rating pain on a visual analog scale (VAS). A 10cm line is drawn with 0 (no pain) on the left pole and 10 (worst pain imaginable) on the right pole. The inventory asks participants to rate their level of pain by placing a slash on the line that best represents their current level of pain as well as pain at its worst, best and average over the past 24 hours. The highest worst pain intensity reported during the intervention will be recorded as the peak pain intensity.

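### The monocyte hypothesis asserts altered migration and MAPK dependence, but the plan measures neither directly and names no expression result that would count for or against them

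*Combined protocol and SAP*

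**What the plan says.** **The hypothesis.** It is stated several times, in different forms.

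- Research Plan, Motivation to study single cells: "Our hypothesis is that CBD alters monocyte migration capacity with MAPK-dependent alterations".
- End of section 4, Background: CBD is expected to act through "MAPK-dependent alterations of monocyte phenotype, reducing their overall migratory" capacity.
- Section 4, in the sentence labelled as the central hypothesis: CBD is beneficial because "it reduces inflammation by hindering pro-inflammatory monocytes via MAPK-dependent pathways". Migration is not mentioned there. A later Background paragraph also gives a MAPK-dependent version without migration.
- Section 5, Specific Aims: the primary aim is to find biomarkers of reduced inflammation that are linked to MAPK-dependent alterations.

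**The measurements.**

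- Aim 2 will quantify the shift in monocytes "by examining gene expression at the single-cell level from the PBMC samples".
- Primary Outcomes: "we will measure RNA expression per single cell (not per patient)".
- CBD biomarker extraction: the expression difference (fold change, p-value, ratio of cell fractions expressing the gene) "will determine the phenotypic effect of CBD".
- Primary Outcomes, on MAPK: "we expect the genes of the MAPK signaling pathway" to be strongly altered.
- Primary Outcomes, on inflammation: "We will regress these gene markers against the variation in baseline inflammation (C-reactive protein, erythrocyte sedimentation rate, and procalcitonin)".
- Experimental Procedures: a blood draw, vital signs and questionnaires at each of three visits, plus urine tests at baseline.

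**The concern.** Migration capacity is something a cell does. Transcript counts in a blood sample can be a surrogate for it but do not observe it. MAPK signalling is carried by the activation state of proteins, which the RNA level of pathway genes does not measure. Dependence on MAPK is a causal statement: it says the effect would not occur, or would differ, if the pathway were blocked. A before-after change in MAPK transcripts, with no comparison arm and no manipulation of the pathway, fits MAPK as the mediator and MAPK as a bystander equally well.

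The stake is interpretation. Section 5 expects these pilot data to lead to larger cohorts. If altered MAPK genes are read as proof of a MAPK-dependent mechanism that reduces migration, a mechanism nobody has demonstrated goes forward as established. If MAPK genes do not change, a mechanism acting through protein activation could be set aside without having been tested.

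**Working it through.** **The plan's own size figure.** Patients × time points × cells per sample: 5 × 3 × 5,000 = 75,000 and 7 × 3 × 5,000 = 105,000, from 5 × 3 = 15 to 7 × 3 = 21 samples. This reproduces the totals under Sample collection and processing. The point does not depend on them, because more cells of the same kind do not change what is being measured. The plan states no alpha, power or effect size, and none is needed here.

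**Each element of the hypothesis against the measurements described.**

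| Element | Where claimed | What the plan describes | Kind of evidence |
|---|---|---|---|
| Monocyte phenotype at RNA level | Background; Aim 2 | Single-cell expression, baseline against months 1 and 2 | Direct |
| Reduced inflammation | Background; Specific Aims | C-reactive protein, erythrocyte sedimentation rate and procalcitonin as regression variables; cytokines named in Aim 2 without an assay | Examinable if the markers are assayed |
| Monocyte migration capacity | End of Background; Motivation to study single cells | No migration or chemotaxis assay | Indirect at most, through migration-related transcripts |
| MAPK pathway action | Background; Specific Aims; Motivation to study single cells | RNA of pathway genes; no protein or phosphorylation measure | Indirect |
| Dependence on MAPK | Same places | No blockade or other manipulation | Association only |

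**Do the non-RNA markers close the gap?** No. They are systemic inflammation markers. Regressing gene markers on them relates expression to inflammation; it does not observe migration or test whether MAPK is required.

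**Is there a criterion for support?** Primary Outcomes expects MAPK genes to be strongly altered. It gives no gene list, direction or threshold, and it does not tie the expectation to one cell type. The end of the Background leaves open which cell population shows the deregulation. For migration, no gene or gene set is named at all.

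**What does the study add to existing evidence?** The Background already reports MAPK-pathway alterations in transcriptome data from people using cannabis, and it describes mediation by MAPK as only possible. The new data add cell-type resolution and within-patient timing. They remain expression-level associations, so they cannot turn possible mediation into dependence.

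**The case against.** The best defence is that this is a discovery pilot whose outcomes largely match its method. The primary outcome is defined as gene expression patterns. The products are called candidates. The primary aim speaks of biomarkers linked to MAPK alterations, and Aim 2 predicts associations. The preliminary MAPK evidence is itself transcriptomic, so MAPK alteration can be read in that sense throughout. All of this stands. It also shows that the discovery work loses nothing if the causal wording is removed.

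Four stronger readings are tempting, and the documents do not support them.

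- A reader might infer that the labelled central hypothesis is about migration. It is not; migration appears only at the end of the Background and under Motivation to study single cells.
- A reader might infer that RNA is the only molecular measurement. Primary Outcomes also names C-reactive protein and procalcitonin, with erythrocyte sedimentation rate.
- A reader might infer that no result could bear on the hypothesis. Expression of MAPK or migration-related genes can lend indirect support or doubt; only a direct test is out of reach.
- A reader might infer that the plan would declare the mechanism proven or rejected. It contains no such rule. Over-interpretation is a risk created by the missing criterion and is not a planned step.

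Aim 2's pairing of macrophages with monocytes adds little, since the same sentence limits the measurement to PBMC samples.

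**Conclusion.** The point holds in a limited form. Migration capacity and MAPK dependence are hypothesised, but neither is measured directly. The planned data can give only indirect, associational evidence on them, and no expression result is named as counting for or against.

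The size is a matter of scope. A count of measured against unmeasured elements would depend on how the hypothesis is divided, so it should not be read as a magnitude. The RNA-level and inflammation parts of the hypothesis are not affected by this point.

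The conclusion rests on two assumptions: that the visit lists and sample-processing text describe all planned assays, and that dependence is meant in its ordinary causal sense. If the investigators mean only that MAPK genes change, the wording should say so, and the same edit serves.

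**What to change.** 1. In section 4, section 5 and Motivation to study single cells, restate the MAPK hypothesis and aim as change from baseline in expression of a prespecified MAPK-pathway gene set in circulating monocytes. The Abstract repeats the aim and should follow.
2. At the end of section 4 and in Motivation to study single cells, drop reduced migratory capacity as a conclusion the study can reach.
3. In CBD biomarker extraction and Primary Outcomes, add the MAPK gene-set score as the read-out, with the gene list and the direction of change that would count as support fixed before the data are seen.
4. In the same two places, add a migration/chemotaxis gene-set score labelled as an exploratory transcriptional surrogate.
5. State that MAPK activation, MAPK dependence and migratory function are left to later functional work.

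The cost is wording plus two scores from data already being collected. The team already uses this kind of tool: the Abstract describes a per-cell inflammation score built from a Gene Ontology term with 556 mouse genes. No new samples, visits or assays are needed. The downside is a more modest mechanistic claim.
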